**11.5.3.4. CAT**

COPD Assessment Test (CAT)
CAT Score

 
The CAT consists of eight items each formatted as a six-point differential scale: 0 (no impact) to 5 (high impact). A CAT score will be calculated by summing the non-missing scores on the eight items with a range from 0 to 40.
 
If one item is missing, then the score for that item is set as the average of the non-missing items. If more than one item is missing, then the CAT score will be set to missing.
 
If the language of the CAT conducted at a post-baseline visit is different to the language used at Day 1 baseline, the CAT score for that visit and all subsequent visits will be set to missing.
 
If there is more than one response to a question at a visit or duplicate questionnaires, the CAT score for that visit will be set to missing.
 

Responder Status according to CAT Score

 
A subject will be considered a responder according to CAT score if their on-treatment CAT score has decreased at least 2 units from the baseline CAT total score.
 
A subject will be considered a non-responder if their on-treatment CAT score has decreased by less than 2 units, has not changed, or has increased compared to baseline.
 
Missing data will be handled as detailed in Section 11.6.
 

CAT Score Categories
The CAT score categories will be defined as: 
 
A score < 10
 
A score <math>\geq</math> 10
 

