**11.5.3.6. BDI/TDI**

**BDI/TDI**

**General**

- The BDI focal score will be calculated as the sum of the ratings recorded for each of the three individual scales (Functional Impairment, Magnitude of Task, and Magnitude of Effort). Each of these scales has five possible scores ranging from 0 to 4 (with lower scores indicating more impairment), with the range of the BDI focal score 0 to 12. If a score is missing for any of the three scales, then the BDI focal score will be set to missing. BDI is assessed at baseline (Day 1).
- The TDI focal score will be calculated as the sum of the ratings recorded for each of the three individual scales (Functional Impairment, Magnitude of Task, and Magnitude of Effort). Each of these scales has a possible score ranging from -6 (major deterioration) to +6 (major improvement). TDI focal score is calculated as the sum of the three individual scores and then

BDI/TDI

divided by 2 (so the range of the TDI focal score is -9 to +9). If a score is missing for any of the three scales, then the TDI focal score will be set to missing.
 
 
• If the language of the TDI conducted at a visit is different to the language for the BDI, all TDI scores at that visit and subsequent visits will be set to missing.
 
• If there is more than one response to a question at a visit or duplicate questionnaires, the BDI or TDI score for that visit will be set to missing.
 

Categorization of TDI Focal Score

 
• Full categorization of TDI focal score for categorical summary is as follows: 
 
‘major improvement’ defined as a score of <math>\geq 7</math> to <math>\leq 9</math>
 
‘moderate improvement’ defined as a score of <math>\geq 4</math> to <math>< 7</math>
 
‘minor improvement’ defined as a score of <math>\geq 1</math> to <math>< 4</math>
 
‘no change’ defined as a score of <math>> -1</math> to <math>< 1</math>
 
‘minor deterioration’ defined as a score of <math>> -4</math> to <math>\leq -1</math>,
 
‘moderate deterioration’ defined as a score of <math>> -7</math> to <math>\leq -4</math>
 
‘major deterioration’ defined as a score of <math>\geq -9</math> to <math>\leq -7</math>
 
 
 

Responder Status according to TDI Focal Score

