**11.5.3.8. EQ-5D-5L**

EQ-5D-5L

 
• If the language of the EQ-5D-5L conducted at a post-baseline visit is different to the language used at baseline, the EQ-5D-5L scores for that visit and all subsequent visits will be set to
 

missing.

- If there is more than one response to a question at a visit or duplicate questionnaires, the EQ-5D-5L health state and utility score for that visit will be set to missing.

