## 11.6. Appendix 6: Handling of Missing Data

Element	Reporting Detail
General	
 
• Missing data occurs when any requested data is not provided, leading to blank fields on the collection instrument:               
 
○ These data will be indicated by the use of a “blank” in subject listing displays unless all data for a specific visit are missing in which case the visit is not displayed in the listing.
 
○ Answers such as “Not applicable” and “Not evaluable” are not considered to be missing data and will be displayed as such.
 
○ Missing data will generally not be considered in the calculation of percentages (i.e., the denominator will not include subjects who have missing data at a given time point).
 
○ No imputation will be made for any missing numerical data, except in the specified sensitivity analyses of the primary and secondary endpoints to assess the impact of missing data on study results.
 
 
 

Responder	
 
• Subjects with a missing baseline will have responder status as missing.
 
• Subjects with missing on-treatment data and a subsequent non-missing on-treatment scheduled assessment will not be considered a responder or non-responder but will be left as missing.
 
• Subjects that have withdrawn from study treatment prior to the visit in question will be imputed as non-responders at all visits post-study treatment discontinuation where the assessment was expected to be performed (regardless of whether the subject has had a post-treatment assessment performed or not). This includes all visits up to and including Week 52.
 
• Subjects with missing on-treatment data and no subsequent non-missing on-treatment scheduled assessments will be imputed as non-responders.
 

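### A duplicate or double-answered CAT or TDI form at Week 52 is voided and then scored as non-response, while the same error at an earlier visit with a later valid score is left missing (minor)

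*SAP*

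**What the plan says.** **Voiding rules.** For CAT (SAP 11.5.3.4), when an item has two answers or there are "duplicate questionnaires, the CAT score for that visit will be set to missing". For dyspnoea (SAP 11.5.3.6), in the same circumstances or with "duplicate questionnaires, the BDI or TDI score for that visit will be set to missing". For EQ-5D-5L (SAP 11.5.3.8), with "duplicate questionnaires, the EQ-5D-5L health state and utility score for that visit will be set to missing"; the VAS is not named. None of these sections separates duplicates that agree from duplicates that conflict.

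**Blank items.** CAT tolerates one: "If one item is missing, then the score for that item is set as the average of the non-missing items". BDI, TDI and the EQ-5D-5L utility do not; any missing scale or dimension already makes the score missing (SAP 11.5.3.6 and 9.1.1.7).

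**Responder status.** The CAT and TDI responder definitions both refer missing data to SAP 11.6, which has three relevant rules:

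- No later score: "Subjects with missing on-treatment data and no subsequent non-missing on-treatment scheduled assessments will be imputed as non-responders".
- A later on-treatment score exists: the subject "will not be considered a responder or non-responder but will be left as missing".
- No baseline: "Subjects with a missing baseline will have responder status as missing".

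**Schedule.** Post-baseline CAT and TDI are taken at Weeks 4, 28 and 52, or at the IP Discontinuation Visit (Protocol 6.2.9 and 6.2.10).

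**The concern.** Imputing non-response is a familiar convention for subjects who stop treatment or do not attend. Here it also reaches a subject who is still on treatment, attended Week 52 and filled in the questionnaire. The only fault is that one item carries two answers or that a second copy exists, possibly identical to the first.

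Because nothing is scheduled after Week 52, the rule that protects an earlier gap can never apply there. The consequence of one clerical error therefore depends on the visit at which it happens.

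The CAT rule has a second oddity: an item with two answers is treated more harshly than an item with none.

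A voided Day 1 CAT or BDI also removes the baseline on which the CAT or TDI models are adjusted, and responder status then becomes missing at every visit.

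At stake is the accuracy of the CAT and TDI responder analyses.

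**Working it through.** The plan gives no rate of duplicate or double-answered forms, so it has no figure to reproduce. The check has two parts.

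**1. Tracing the rules.** Take a CAT responder with an assumed baseline of 20 and scores of 15, 15 and 12 at Weeks 4, 28 and 52. The SAP threshold is a fall of at least 2 units. Void one visit at a time and apply SAP 11.6:

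| Form voided | Week 4 | Week 28 | Week 52 |
|---|---|---|---|
| None | responder | responder | responder |
| Week 4 | missing | responder | responder |
| Week 28 | responder | missing | responder |
| Week 52 | responder | responder | **non-responder** |
| Day 1 | missing | missing | missing |

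TDI follows the same path with its own threshold (focal score at least 1 unit). An earlier visit is also recoded if every later one is missing.

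**2. Size under assumed rates.** Inputs: 4,000 subjects per arm (the planned FF/UMEC/VI and FF/VI arms); assumed true Week 52 responder proportions p of 45% and 40%; an assumed share d of Week 52 forms voided, equal in both arms.

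- Observed proportion = p × (1 − d)
- Responders recoded = 4,000 × p × d
- Odds ratio = [p1(1 − d) / (1 − p1(1 − d))] ÷ [p0(1 − d) / (1 − p0(1 − d))]

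| d | Observed proportions | Responders recoded | Odds ratio |
|---|---|---|---|
| 0 | 45.0% and 40.0% | 0 and 0 | 1.227 |
| 0.5% | 44.8% and 39.8% | 9 and 8 | 1.226 |
| 1% | 44.6% and 39.6% | 18 and 16 | 1.225 |
| 2% | 44.1% and 39.2% | 36 and 32 | 1.224 |
| 5% | 42.8% and 38.0% | 90 and 80 | 1.218 |

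At d = 2%, for example, (0.441/0.559) ÷ (0.392/0.608) = 0.7889 ÷ 0.6447 = 1.224. Power for a two-sided 5% comparison of the two proportions falls from 0.995 at d = 0 to 0.991 at d = 5%.

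If the voiding rate differed by arm, the shift could go either way. With 1% voided in the better arm and 2% in the other, the odds ratio is 1.246; with the rates reversed it is 1.203.

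The 4,000 figure suits CAT in the two larger arms. It is only an upper bound for TDI, which is collected in a subset of subjects at selected sites, and the UMEC/VI arm is planned at 2,000.

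**The case against.** The strongest reply is that this hardly matters. With equal rates in the arms, even 5% voided forms move the odds ratio by less than 0.01. CAT and TDI responder rates are other efficacy endpoints with unadjusted p-values, outside the testing hierarchy. Both instruments also have repeated-measures analyses in which a voided post-baseline score simply stays missing. SAP 11.2.1 says that questionnaires from subjects stopping at a scheduled visit are reported on a Logpad. Such a record is moved into the scheduled visit only if that visit has none, which removes one foreseeable source of duplicates; electronic entry may also make double answers rare. All of this stands, and it sets the severity.

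A second reply is that voiding is pre-specified, applies equally to all arms, and avoids choosing between forms. That holds for forms that conflict, and for a BDI or TDI scale with two answers. It does not hold for duplicates that agree, or for CAT, where the SAP already has a way to score a form with one unusable item.

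A third reply is that SAP 11.6 opens by describing missing data as blank fields, which a duplicate form is not. But these scores are expressly made missing, and both responder definitions point to 11.6. If another reading was meant, it should be written down.

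The eDiary rule (SAP 11.5.3.7) keeps duplicate daily records, and a reader might infer that questionnaires should be handled likewise. That goes too far. The eDiary rule takes the worst value, which is in the spirit of imputing non-response, and a worst daily count does not settle which of two multi-item forms is valid. It shows only that a rule for duplicates can be specified.

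**Conclusion.** The point holds as a minor one. The SAP's rules, read together, misclassify an on-treatment subject whose completed Week 52 CAT or TDI form shows a response but contains a double answer or has a duplicate. The CAT rule is internally inconsistent as well. A voided Day 1 CAT or BDI removes the subject from the baseline-adjusted models for that instrument.

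The size rests on assumed response and voiding rates, since the documents give neither. On those assumptions the effect on the treatment comparison is very small unless voiding differs by arm, and nothing in the documents suggests that it does.

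Three stronger conclusions that a reader might draw are not supported:

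- **That the primary endpoint or the hierarchy is affected.** Exacerbation counts come from the eCRF, and SGRQ, the patient-reported endpoint in the hierarchy, follows its own manual for multiple responses (SAP 11.5.3.3).
- **That EQ-5D-5L suffers the same misclassification.** It has no responder analysis and is only summarised, so it loses descriptive utility data.
- **That valid data are always discarded.** Two conflicting forms, or a scale with two answers, have no determinate score.

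**What to change.** Before unblinding, amend the SAP as follows:

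1. **SAP 11.5.3.4:** treat a double-answered CAT item as a missing item under the existing one-item rule.
2. **SAP 11.5.3.4 and 11.5.3.6:** keep the score when duplicate forms agree. For conflicting forms, state one rule in advance, for example the first completed form if time stamps exist, otherwise missing. The SAP does not document questionnaire time stamps, so their availability must be confirmed first. The same sentence can be added to 11.5.3.8 for consistency.
3. **SAP 11.6:** state that an on-treatment score voided by a data-quality rule is left missing and is not imputed as non-response.

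The cost is a few sentences and small programming changes. Items 1 and 3 and the agreeing-duplicates part of item 2 need no new data. The downside is that a small number of subjects are left missing at Week 52 instead of receiving the worst-case value. The synopsis places final-analysis decisions at Source Data Lock, before database freeze, so the change can be made blind.

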**11.5.3.5. All Cause Mortality**

Rate of all cause mortality
The raw event rate per thousand subject-years for adjudicated deaths will be calculated as the number of events x 1000 divided by the at risk period during the time-period of interest as defined in Section 11.5.1.5.1.
Time to On-treatment All Cause Mortality

 
The time to on-treatment all cause mortality will be calculated as death date – date of start of treatment + 1.
 
Subjects will be represented from their Day 1 date to the date of death (on-treatment) or date of censoring. Subjects that have not experienced an on-treatment death are censored as follows:
 

- Subjects that have completed the study are censored at the earliest of (date of study conclusion and date of study treatment stop + 7 days).
- Subjects that have an off-treatment or post-study death reported are censored at the date of their study treatment stop + 7 days
- Subjects that prematurely withdraw from the study and have a survival status present are censored at the earliest of (date last known alive and date of study treatment stop + 7 days)
- Subjects that prematurely withdraw from the study and do not have a survival status reported at 52 weeks post-randomisation are censored at the earliest of (date of study conclusion and date of study treatment stop + 7 days)

**Time to On and Off-treatment All Cause Mortality**

- The time to on and off-treatment all cause mortality will be calculated as death date – date of start of treatment + 1.
- Subjects will be represented from their Day 1 date to the date of death (on and off-treatment, as defined in Section 11.3.2) or date of censoring. Subjects that have not experienced an on or off-treatment death are censored as follows:
  - Subjects that have completed study treatment are censored at the earliest of (date of study conclusion and date of study treatment stop + 7 days).
  - Subjects that prematurely discontinued study treatment that attended the Week 52 visit are censored at the earliest of (date of study conclusion and date of Week 52 + 7 days).
  - Subjects that prematurely discontinued study treatment that withdrew from the study prior to Week 52 and have a survival status present are censored at the earliest of (date last known alive and projected Week 52 date + 7).
  - Subjects that prematurely discontinued study treatment that withdrew from the study prior to Week 52 and do not have a survival status present or that have a post-study death reported are censored at the earliest of (date of study conclusion and projected Week 52 date + 7).

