**11.3.2. All Cause Mortality**

For the summaries and analyses of the efficacy endpoint of all cause mortality, treatment phases will be defined as described in the table below after any imputation of partial death dates as described in Section 11.6.1:

Pre-treatment	Death Date < Treatment Start Date (i.e. subject did not start study treatment)
On-treatment	Treatment Start Date ≤ Death Date ≤ Treatment Stop Date + 7
Off-treatment	Subjects that prematurely discontinued study treatment that attended the Week 52 visit: Treatment Stop Date + 7 < Death Date ≤ date of Week 52 + 7  Subjects that prematurely discontinued study treatment that withdrew from the study prior to Week 52: Treatment Stop Date + 7 < Death Date ≤ projected Week 52 date + 7
Post-study	Subjects that completed study treatment: Death Date > Treatment Stop Date + 7  Subjects that prematurely discontinued study treatment that attended the Week 52 visit: Death Date > date of Week 52 + 7  Subjects that prematurely discontinued study treatment that withdrew from the study prior to Week 52: Death Date > projected Week 52 date + 7
Note: Study treatment completion is defined in Section 11.5.1.3. The projected Week 52 date is defined in Section 11.5.1.4.	

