**11.3.3. Other Data**

**11.3.3.1. Post-treatment and Post-study Phases**

For all events and assessments the post-treatment and post-study phases will be defined as follows:

Post/Off-treatment	Event Onset Date or Assessment Date ≥ Treatment Stop Date + 2 AND Event Onset Date or Assessment Date ≤ study conclusion date  Note: the study conclusion date reflects the safety F/U contact for study treatment completers or the maximum of (the subjects last phone contact or their last clinic visit or the date the subject was lost to follow-up) for those subjects who discontinued study treatment prematurely.
Post-study	Event Onset Date or Assessment Date > study conclusion date.  Note: this post-study data will not be included in any summaries or analyses (but will be listed)

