#### 11.5.1.4. Projected Week 52 Date

For those subjects who have withdrawn from the study prior to Week 52, a projected Week 52 date will be derived as follows:

Projected Week 52 Date = Date of randomisation + 52 weeks

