#### 11.5.1.5. At Risk Period for Calculation of Raw Event Rate

##### 11.5.1.5.1. All Cause Mortality

For calculations of raw event rate the 'at risk period' in years (used for the denominator) will be defined as follows:

- On-treatment at risk period:
  - For subjects that completed the study up to Week 52 the on-treatment at risk period will derived as:  
(minimum (date of end of study treatment + 7, date of death, date of study conclusion) – date of start of treatment + 1)/365.25
  - For subjects that prematurely withdrew from the study prior to Week 52 and that have a survival status reported the on-treatment at risk period will derived as:  
(minimum (date of end of study treatment + 7, date of death, date last known alive) – date of start of treatment + 1)/365.25
  - For subjects that prematurely withdrew from the study prior to Week 52 and that do not have a survival status reported the on-treatment at risk period will derived as:  
(minimum (date of end of study treatment + 7, date of death, date of study conclusion) – date of start of treatment + 1)/365.25
- On and off-treatment at risk period:
  - For subjects that did not prematurely discontinue study treatment the on and off-treatment at risk period will derived as:  
(minimum (date of end of study treatment + 7, date of death, date of study conclusion) – date of start of treatment + 1)/365.25
  - For subjects that prematurely discontinued the study treatment period and completed the study up to Week 52 the on and off-treatment at risk period will derived as:  
(Date of study conclusion – date of start of treatment + 1)/365.25
  - For subjects that prematurely discontinued the study treatment period and prematurely withdrew from the study prior to Week 52 the on and off-treatment at risk period will derived as  
(minimum(Date last known alive, Date of Death, Projected date of Week 52 (as defined in Section 11.5.1.4) + 7) – date of start of treatment + 1)/365.25
  - For subjects that prematurely withdrew from the study prior to Week 52 and that do not have a survival status reported the on and off-treatment at risk period will derived as:  
(Date of study conclusion – date of start of treatment + 1)/365.25

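### On- and off-treatment mortality: a withdrawn subject with a death after the Week 52 + 7 window is censored at withdrawal, although known alive for the whole window

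*SAP*

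**What the plan says.** SAP 11.3.2 sets the mortality window. For a subject who stopped treatment early and withdrew before Week 52, an off-treatment death, which counts as an event, satisfies "Treatment Stop Date + 7 < Death Date ≤ projected Week 52 date + 7". The date of withdrawal plays no part. A post-study death satisfies "Death Date > projected Week 52 date + 7". SAP 11.5.1.4 fixes the anchor: "Projected Week 52 Date = Date of randomisation + 52 weeks".

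SAP 11.5.3.5, under Time to On and Off-treatment All Cause Mortality, gives two censoring rules for such subjects when no death falls in the window:

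- Those who "have a survival status present are censored at the earliest of (date last known alive and projected Week 52 date + 7".
- Those who "do not have a survival status present or that have a post-study death reported are censored at the earliest of (date of study conclusion" and the projected Week 52 date plus 7 days).

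For a subject who stopped treatment early, SAP 11.3.3.1 takes the study conclusion date as "the maximum of (the subjects last phone contact or their last clinic visit or the date the subject was lost to follow-up").

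The on-treatment mortality analysis in the same section treats later deaths differently: "Subjects that have an off-treatment or post-study death reported are censored at the date of their study treatment stop + 7 days".

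**The concern.** The second rule puts two different kinds of subject together. For one, nothing is known after withdrawal, and censoring there is right. For the other, a post-study death shows that the subject was alive on every day of the window, and censoring at withdrawal discards that knowledge.

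Follow-up inside the window then depends on something that happens after it has closed. Of two subjects who withdraw on the same day and are both known alive past the window, the one whose later death is reported gets less follow-up. Deaths between withdrawal and the end of the window are still counted as events, so information obtained after withdrawal is used when it is an in-window death and set aside when it is survival followed by a later death. At stake is the internal consistency of the Cox and Kaplan-Meier mortality results, and possibly their agreement with the raw mortality rate.

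**Working it through.** The SAP states no figure that depends on this rule, so the check applies the rules to example subjects.

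**Inputs.** Take treatment start as the day of randomisation and count days from start. The window closes at 52 × 7 + 7 = 371 days (11.5.1.4, 11.3.2). Time in the analysis is date − start + 1 (11.5.3.5), so complete follow-up is 371 + 1 = 372 days, or 372 / 365.25 = 1.018 years. For a subject who withdrew before Week 52, study conclusion precedes the close of the window (11.3.3.1), so the minimum in the second rule is the withdrawal date.

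**Three subjects who all withdraw at day 150:**

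| What is learned later | Rule | Cox/Kaplan-Meier follow-up |
|---|---|---|
| Recorded alive at day 390 | min(390, 371) + 1 | 372 days, censored |
| Dies at day 400 (post-study, since 400 > 371) | min(150, 371) + 1 | 151 days, censored |
| Dies at day 300 (off-treatment, since 300 ≤ 371) | 300 + 1 | 301 days, event |

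The first two were both alive at day 371. Their follow-up differs by 372 − 151 = 221 days, or 221 / 365.25 = 0.605 years. In general the loss is 371 − w days for withdrawal at day w: 341 days at w = 30, 191 at w = 180, 101 at w = 270 and 21 at w = 350.

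**Raw-rate denominator (11.5.1.5.1) for the subject who dies at day 400.** Two on- and off-treatment rules could apply.

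- The rule for early discontinuers who withdrew takes "minimum(Date last known alive, Date of Death, Projected date of Week 52" plus 7 days). With no earlier last-known-alive date this is min(400, 371) + 1 = 372 days, against 151 in the Cox analysis. If a last-known-alive date of day 150 is on file, it is min(150, 400, 371) + 1 = 151 days, and the two agree.
- The rule for withdrawn subjects without a reported survival status uses study conclusion: 150 + 1 = 151 days, and again the two agree.

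**Size.** Person-years lost = n × (371 − w) / 365.25 for n affected subjects. Neither n nor w is in the documents. The total of 10,000 person-years is also an assumption (10,000 subjects for about one year).

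| n (assumed) | w (assumed) | Person-years lost | Share of 10,000 |
|---|---|---|---|
| 5 | 350 | 0.3 | 0.003% |
| 5 | 180 | 2.6 | 0.03% |
| 20 | 180 | 10.5 | 0.1% |
| 100 | 30 | 93.4 | 0.9% |

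The last row is a deliberate extreme.

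**After the fix.** A withdrawn subject with a post-study death has 372 days whatever the withdrawal day, the same as a withdrawn subject confirmed alive beyond the window.

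**The case against.** The strongest counter-argument is that the repair also lets follow-up depend on a future death. Withdrawn subjects of unknown status would stay censored at study conclusion, while those with a reported late death would be credited to the end of the window. The protocol asks sites only for survival status at the end of the planned 52 weeks (3.1, 4.5.1), so later deaths come to light incidentally, and ignoring incidental information can be defended. This would carry weight if the analysis ignored all post-withdrawal information. It does not: a death after withdrawal and inside the window is an event. Having accepted that information, the analysis should also accept known survival. What stands is that subjects of unknown status remain a limitation under either rule.

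The contrast between two withdrawn subjects also needs the living one to have a last-known-alive date beyond withdrawal. If that date is the withdrawal date, both are censored there. And the two censoring rules overlap for a subject with both a survival status and a post-study death, although only the second names the death.

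Three stronger readings are tempting, and the documents do not support them.

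- A reader might infer that the Cox analysis and the raw rate necessarily use different follow-up for the same person. That depends on which 11.5.1.5.1 rule applies and on whether an earlier last-known-alive date exists. The on-treatment denominator for subjects with no survival status also lists date of death, so the SAP appears to allow a known death without a survival status.
- A reader might infer that time is removed from the sickest subjects. By definition these subjects outlived the window; those who died within it are events.
- A reader might infer a biased treatment comparison. Losing event-free time while keeping events pushes estimated mortality slightly upward, but nothing in the documents suggests that the loss would differ by arm.

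**Conclusion.** Wrong as written, and small. Under 11.3.2 a withdrawn subject with a post-study death is known alive for the whole window, and 11.5.3.5 censors that subject at withdrawal solely because of the later death. This follows from the SAP's definitions and needs no assumption about the data. Partial death dates do not weaken it: 11.6.1 imputes them to 1 January, or to the latest contact date if that is later, and 11.3.2 classifies the death after imputation.

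The size does rest on assumptions, because the number affected and their withdrawal times are unknown. Over the ranges tried the loss is 0.003% to 0.9% of follow-up, and most plausibly well under 1%. Time to death is listed among the other efficacy endpoints (SAP 2.2) and shown with unadjusted p-values only (9.1.2.9), and no comparison in the testing hierarchy (11.9) uses it. Disagreement with the raw rate is possible but not certain; the firm finding there is that 11.5.1.5.1 does not say which rule covers this subject.

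**What to change.** Split the last censoring bullet under Time to On and Off-treatment All Cause Mortality in SAP 11.5.3.5. Leave withdrawn subjects with no survival status as they are. Give subjects who withdrew before Week 52 and have a post-study death their own rule: censored at the projected Week 52 date + 7 days, whatever their survival-status entry. State the same end date for these subjects in the on- and off-treatment at-risk period of 11.5.1.5.1, so that the Cox, Kaplan-Meier and raw-rate results share one follow-up time.

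The cost is one sentence in each section and a line of derivation code for each quantity. It uses dates already collected and changes no data collection, endpoint or model.
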